3.6 Data collection

3.6.1 Sample description measures

Data will be gathered about the demographic characteristics of both members of the couple, including protected characteristics. Information about the injury, specifically the type of injury and the date of its occurrence, will also be collected. To obtain a measure of the level of disability caused by the injury, the non-injured partner will be asked to complete the *European Brain Injury Quest*ionnaire ⁵⁹. These data will be

obtained during the second recruitment interview once informed consent has been given. Documents will be identified using a unique code for each participant, and will not contain their names.

3.6.2 Interviews with the therapists and the participants

Each couple will be interviewed once their course of 10 sessions is complete. Each therapist will also be interviewed twice during the period of the project. Interviews will be conducted by a psychologist employed for the purposes of the project and tasked with the evaluation of the therapy.

The interviews will be semi-structured. Questions for the couple will address:

- their general experience of the therapy
- what they found helpful
- whether there was anything that was less helpful
- whether there was anything upsetting, distressing or demanding about the therapy
- suggestions for improvements
- their understanding of what the therapy's aims were and whether those aims were meaningful to them as a couple (i.e. credibility)
- circumstances that might have impacted on therapy effectiveness
- whether, overall, they felt they benefited from the therapy

Similarly, questions for the therapists will address:

- their general experience of the therapy
- what aspects of the therapy they thought were beneficial, and why
- what aspects were less helpful
- whether any aspect of the therapy was upsetting, distressing or too demanding for one or more couples
- any suggestions for improvements
- whether the rationale for the therapy was convincing, given their experience of applying it
- what factors may have had an impact on the effectiveness or ineffectiveness of the therapy

Interviews will typically be face-to-face and conducted at the venue where the couple received the therapy sessions. There will also be the option of interviews by telephone or on-line, using a secure service such as Zoom or Microsoft Teams and an NHS-authorised account. Interviews will be semi-structured, using a set list of questions, and will be audio-recorded using an encrypted device. The recording will be transcribed by the person who conducted the interview. No specific identifying details (such as names and places) will be included in the transcription. A unique code for each participant will be used to identify transcripts.

3.6.3 Measures of mechanism and outcome

Participants will complete a set of questionnaires before and after they have received the therapy. The questionnaires will be administered by the psychologist recruited for the purpose of evaluating the therapy (see Section 3.9 below). Questionnaires will be completed on paper. Names will not appear on the questionnaires which will be identified with a unique code for the participant. Participants will be required to complete the questionnaires separately and not to discuss the content or show the completed questionnaires to one another.

In accordance with MRC recommendations about evaluating complex interventions⁴⁴, the mechanisms whereby the intervention is expected to have its effect will be assessed as well as the outcomes themselves. In the present case, the therapy is expected to enhance continuity in self-identity and the relationship, and increased continuity is expected to lead to a range of beneficial outcomes.

Based on research described in Section 1.2 and Section 1.3, several benefits are expected. The questionnaires will not address all of these potential benefits because validated questionnaires are not available. Questionnaires marked with an asterisk* will only be administered before the therapy; questionnaires marked with a caret^ will only be administered after the therapy.

The injured partner will complete:

- Background:
 - o Demographic information and questions relating to the brain injury*
- Mechanisms
 - o Continuity of Self-Identity Questionnaire⁷⁴ measure of continuity in self-identity
- Outcomes:
 - o Rosenberg Self-Esteem Scale 16,66 self-esteem
 - Warwick-Edinburgh Mental Wellbeing Scale 58 and Depression, Anxiety and Stress Scale2 general psychological wellbeing
 - o Index of Marital Satisfaction⁷² relationship quality and satisfaction with the relationship
- Therapy:
 - Two questions relating to their experience of the therapy itself^

The non-injured partner will complete:

- Background:
 - Demographic information and questions relating to the brain injury*
 - European Brain Injury Questionnaire, informant version⁵⁹ *- questions about the impact of the injury on the person with the brain injury
- Mechanisms
 - o *Birmingham Relationship Continuity Measure for Acquired Brain injury*⁶⁷ experience of continuity in the relationship.
- Outcomes:
 - The *Head Injury Behaviour Rating Scale*⁵⁵ extent to which changes in the person with the brain injury are perceived as distressing and burdensome.
 - Warwick-Edinburgh Mental Wellbeing Scale 58 and Depression, Anxiety and Stress Scale2 general psychological wellbeing and anxiety
 - o Index of Marital Satisfaction⁷² relationship quality and satisfaction with the relationship.

Version date:

21.11.2023

13 of 24

Page:

- Therapy:
 - o Two questions relating to their experience of the therapy itself^

3.6.4 Report Form

A report form will be developed with sections for recording:

- comments about what they found helpful / unhelpful
- suggestions about improvements
- whether the demands of the therapy are unreasonable
- whether anything was upsetting or distressing
- ideas about contextual factors that might impact on effectiveness

Participants will be given a copy of this form and asked to add comments as appropriate. At an appropriate point near the end of the therapy, the therapist will set aside some time to discuss with the participants any comments entered onto this form and whether they have any other thoughts about these issues.

The therapists will also have a copy of the same form with additional sections addressing:

- any adverse events experienced by the couple during the time of their participation, whether these
 are related to the therapy or not
- issues about the clarity of the guidelines (for the therapist only)

3.7 Participant withdrawal

If, at any point during their participation, one or both members of the couple express a wish to withdraw, their wish will be respected. They will be given the opportunity to discuss the reasons for withdrawal, but it will be made clear to them that they are under no obligation to explain themselves if they do not wish to do so. The researcher will not make any attempt to change their decision. If only one member of a couple wishes to withdraw, the couple will be withdrawn from the research. The therapist will not provide any further intervention for the person who does not wish to withdraw.

The aim is to recruit and deliver the full course of therapy to 10 couples. Consequently, if a person or couple drop out, another couple will be recruited, and this will continue until at least 10 couples have completed the full course.

Participants who withdraw prematurely will not be asked to complete any questionnaires or provide any further information following their decision to withdraw. However, any relevant information previously obtained from the report form and the pre-therapy questionnaires provided by these participants will be retained and included in the evaluation of the therapy.

3.8 Data analysis

For the mechanism and outcome questionnaires, the Reliable Change Index⁴¹ will be used to compare pre- and post-therapy scores for each participant to determine whether there is any statistically reliable improvement on each questionnaire. The criterion of ± 1.645 will be used as recommended for use when comparing scores in individual cases⁷³.

For analysing the data from the interviews and the report forms, framework analysis will be used²¹. This technique is suitable for the proposed study because it allows one to structure the analysis according to preset categories of interest (e.g. what participants found helpful or unhelpful) but also provides an opportunity to develop more specific novel themes within these broader pre-set categories (e.g. participants might find the intervention too directive). The analysis provides a systematic way of grouping and summarising the data. A key feature is a matrix composed of participants (rows) and categories/themes (columns) into which specific excerpts from the data are inserted. In accordance with framework analysis²¹, an initial list of categories will be used to code the data from the first three participants. The categories/themes will then be modified as necessary and used to code data from subsequent interviews and report forms, but will be continually updated to accommodate any new themes.

3.9 Separation of therapy delivery and data collection/analysis

A psychologist will be employed specifically to conduct the interviews and to administer the pre- and post-intervention questionnaires, and will take no part in administering the therapy. Participants are likely to feel more comfortable about criticising the therapy if the interviews and questionnaires are administered by a different person. To further promote separation of the delivery and evaluation of the therapy, the conduct

Version date:

21.11.2023

14 of 24

and analysis of the interviews and questionnaire data will be supervised by a co-investigator who will not be involved in delivering therapy ([name]).

3.10 Decision about progression

One aim of the project is to collect information to enable a decision about whether a subsequent controlled evaluation of the therapy is merited. Several sources of information will be used in making this decision:

- Participants will complete questionnaires before and after the therapy (Section 3.6.3). Although this
 will not provide evidence of the therapy's effectiveness, a failure to observe any statistically reliable
 improvement in these outcomes would suggest that there is no merit in pursuing its controlled
 evaluation.
- At the end of therapy, participants will complete a brief questionnaire containing two items about their experience of the therapy (Section 3.6.3). Information about this will also be gathered from the interviews and report form (Sections 3.6.2 and 3.6.4). The number of couples who prematurely withdraw from the study is also relevant. If the therapy is assessed poorly in these terms, this would raise questions about the value of further evaluation.
- Information about contextual factors impacting on effectiveness will also be gathered from the interviews and report forms. This information is relevant to the decision because it may help explain a poor response.

In making the decision about progress, there are several issues that need to be considered. First, it is important that the therapy impacts on both the hypothesised mechanism (an increase in the sense of continuity) and the outcomes⁴⁴. An improvement in outcome without any change in the mechanism would suggest that the benefits occurred for some other reason; and an improvement in the mechanism without change in outcome would suggest that the theory underlying the therapy is incorrect. Second, if the majority of the sample of 10 couples were, by chance, influenced by contextual factors that adversely impacted on effectiveness, then a decision not to progress on the basis of a relatively poor average response might be premature. Third, there is a possibility that the therapy might be beneficial for the non-injured partner but less so for the injured partner (or vice versa). In this case, it might be worth progressing to a controlled evaluation of a version of the therapy that focused more on one partner.

Taking these issues into consideration, progression will occur if all three of the following conditions are met:

- More than half of the 20 participants who complete the therapy (= 10 couples) show statistically reliable improvement on both a hypothesised mechanism of effect and an outcome measure.
- More than half of these 20 participants give positive ratings to the therapy on the brief questionnaire about their experience of the therapy.
- Fewer than half of the couples who start the therapy decide to withdraw before the end.

An exception to this decision process will be considered if the information collected about contextual factors provides a plausible explanation of why all three conditions were not met, and thereby provides a plausible basis for expecting that, with better-informed selection criteria or methods of implementation, the therapy could prove effective.

4. Safety reporting

At the start of each therapy session, the therapist will ask the couple about any adverse events that have occurred since the previous meeting. The therapist will immediately notify the Chief Investigator of any serious adverse events (i.e. any event requiring intervention from NHS or Social Care services or third-sector equivalent, or any serious fracture in the relationship such as one person moving out of the shared home). The Chief Investigator will make a decision about whether this may be causally connected to the intervention (i.e. a serious adverse reaction). Notifications and decisions will be recorded and, in the event of a serious adverse reaction, a meeting of the Project Advisory Group will be convened and will make a decision about how to proceed (i.e. whether to stop further delivery of any therapy or to make amendments to the protocol and/or the guidance for its delivery).

Delivery of the therapy to 10 couples will be spread over an 18-month period. The outcomes for each couple will be reviewed at the end of their therapy. The trial will be prematurely terminated if the first 5 couples show little benefit from the therapy, there have been one or more serious adverse reactions, and there is no plausible explanation for these findings and therefore no realistic prospect of making changes to the delivery of the therapy in order to improve outcome.

5. Ethical and regulatory considerations

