3.1 Overview

The aims will be achieved in the context of delivering the therapy to 10 couples. An initial version of the guidelines for delivering the therapy will be produced that incorporate the new elements identified in the literature review (Aim 1). This version will be used to deliver the therapy to the first three couples that take part in the study. Therapists and participants will be interviewed about their experience of the therapy (Aims 1, 2 and 3). Based on this feedback and data from a Report Form, further changes and refinements will be made to the guidelines. The revised guidelines will be used for the next three couples. Further revision will be considered after six couples have completed. Dependent on whether the therapy will be taken forward for formal evaluation, the guidelines will be revised and finalised at the end of the study (Aim 5). Before and after

Version date:

21.11.2023

8 of 24

the therapy, participants will complete questionnaires evaluating their perceptions of continuity, their psychological wellbeing and the quality of their relationship. Although this will not provide evidence of the therapy's effectiveness, a lack of improvement would suggest that there is no merit in pursuing its controlled evaluation (Aim 4).

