The West Midlands is an area of significant socioeconomic and cultural diversity, and every effort will be made to recruit a diverse sample. The NHS Trust hosting the research has a *Community Connexions Programme* and a *BAME network* that can be used as routes for reaching diverse communities. No protected characteristic will disadvantage potential participants in terms of recruitment except in the circumstance that a person's disability is so severe that they are unable to give informed consent or take a meaningful part in verbal therapy. It is acknowledged, however, that the small sample size precludes recruitment of a sample that is properly representative of the West Midlands area.

Inclusion criteria

- Couples must be living together at the time of participation.
- Couples must have lived together for at least 2 years before the injury. The concept of continuity/ discontinuity in the relationship has less application if the pre-injury relationship was brief.
- The injury must have occurred at least 1 year previously. The therapy is focused on what happens after the person with the injury develops an awareness of the effects of the injury and this may take some time to develop. Relationship difficulties also typically take some time to emerge.
- The injury must have occurred no more than 10 years previously. Continuity would be difficult to establish if the pre-injury identity and relationship are too far in the past.
- One or both partners must report some dissatisfaction with their current relationship.
- Both participants are over the age of 21. There is no upper age limit.

Exclusion criteria

- Participants must report that the pre-injury relationship was at least satisfactory. It makes little sense to try to reconnect with an unsatisfactory pre-injury relationship.
- Both participants must be capable of giving informed consent and taking part in verbal therapy.
- One or both members of the couple find it difficult to participate in verbal therapy conducted in English.
- There are co-morbid serious mental or physical health conditions for either partner that may impact on their meaningful participation.
- Staff in the service from which participants are recruited have serious concerns about the psychological wellbeing of one or both members of the couple, or about the fragility of their relationship.

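### The progression rule in Section 3.10 says it allows for benefit mainly in one partner, but its pooled threshold of 11 out of 20 cannot be met by one partner role alone

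*Protocol*

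**What the plan says.** Section 3.10 lists three issues to weigh before setting the progression rule. The third is that "there is a possibility that the therapy might be beneficial for the non-injured partner but less so for the injured partner", or the other way round. In that event the protocol says it might be worthwhile to take forward a version directed more at one partner.

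The rule is then introduced with "Taking these issues into consideration, progression will occur if all three of the following conditions are met". The conditions are:

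- **Condition 1:** "More than half of the 20 participants who complete the therapy (= 10 couples) show statistically reliable improvement". To count, a participant must improve on a mechanism measure as well as on an outcome.
- **Condition 2:** "More than half of these 20 participants give positive ratings to the therapy". These ratings come from the two-item form completed after therapy.
- **Condition 3:** fewer than half of the couples who begin therapy withdraw early.

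An exception may be considered if information on contextual factors plausibly explains why the conditions were not met, and better selection or implementation could be expected to make the therapy work.

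On numbers, Section 3.7 says "The aim is to recruit and deliver the full course of therapy to 10 couples", with replacement of couples who drop out. That gives 10 injured and 10 non-injured partners.

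**The concern.** Each of the three listed issues should be traceable in the rule. The first (mechanism and outcome must both move) is built into condition 1. The second (adverse contextual factors) is built into the exception clause. The third (benefit mainly in one partner) appears nowhere, because conditions 1 and 2 count participants without regard to role.

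This matters because the two roles have separate rationales (Sections 1.2 and 1.3) and different mechanism measures (Section 3.6.3): continuity of self-identity for the injured partner and continuity of the relationship for the non-injured partner. A split by role is therefore a natural pattern to look for, and the protocol itself anticipates it.

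The progression decision is Aim 4 of the study. If results do split by role, the rule as written returns a negative answer. Any one-partner route would then have to be devised after the data were seen, which would be hard to defend.

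**Working it through.** **Inputs from the protocol**

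- 10 couples give 10 × 2 = 20 participants, 10 in each role (Sections 3.7 and 3.10).
- Conditions 1 and 2 each require more than half of the 20, pooled over roles (Section 3.10).
- All three conditions must be met (Section 3.10).

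**Inputs assumed**

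- The protocol gives no response rates by role. I use 0.6 to 1.0 in the role that benefits and 0.1 to 0.3 in the other, plus 0 for the extreme case.
- Partners within a couple are treated as independent.
- Exactly 10 couples complete.

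The protocol gives no power calculation to reproduce, since the number of couples is set by budget (Section 3.4). The stated denominator of 20 is reproduced by the count above.

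**Step 1: the threshold.** Half of 20 is 10, so more than half means at least 11.

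**Step 2: benefit in one role only.** The most that one role can contribute is 10.

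- Non-injured 10/10 and injured 0/10: 10/20, not more than half, so condition 1 fails.
- The mirror case fails in the same way.
- With no responder in one role, condition 1 cannot be met at any response rate in the other.

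Condition 2 has the same structure, so it also fails if positive ratings are confined to one role.

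**Step 3: benefit in one role, less in the other.** Splits such as 10+1, 9+2, 8+3 and 7+4 total 11 and pass. To see how often such splits would arise, let X ~ Bin(10, p_a) and Y ~ Bin(10, p_b). Then

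P(meet condition 1) = P(X + Y ≥ 11) = Σ P(X = i) · P(Y ≥ 11 − i).

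At p_a = 0.9 and p_b = 0.1 the main terms are:

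- i = 10: 0.3487 × 0.6513 = 0.2271
- i = 9: 0.3874 × 0.2639 = 0.1022
- i = 8: 0.1937 × 0.0702 = 0.0136
- i = 7 and below: about 0.0008

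The total is 0.344. The same sum at other assumed rates is below. The last column is the chance that the benefiting role, taken alone, has at least 6 of 10 responders.

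| Rate, benefiting role | Rate, other role | Meets condition 1 as written | Benefiting role reaches 6 of 10 |
|---|---|---|---|
| 1.0 | 0.1 | 0.651 | 1.000 |
| 0.9 | 0.1 | 0.344 | 0.998 |
| 0.8 | 0.1 | 0.165 | 0.967 |
| 0.8 | 0.2 | 0.388 | 0.967 |
| 0.8 | 0.3 | 0.604 | 0.967 |
| 0.7 | 0.1 | 0.070 | 0.850 |
| 0.6 | 0.1 | 0.026 | 0.633 |

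**Step 4: the price of a role route.** Suppose progression of some kind is open if either role reaches 6 of 10 or the pooled count reaches 11. A pooled count of 11 forces at least one role to 6 or more, because 5 + 5 = 10. The combined chance is therefore 1 − (1 − P(Bin(10, p) ≥ 6))² at a common rate p.

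- p = 0.3: 1 − (1 − 0.0473)² = 0.092, against 0.017 for the pooled rule alone.
- p = 0.5: 1 − (1 − 0.3770)² = 0.612, against 0.412 for the pooled rule alone.

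**The case against.** **The protocol speaks of less benefit, not none, and only says progression might be worthwhile.** This stands. A reader might infer that Section 3.10 flatly contradicts itself, but the text does not support that. The one-partner passage is permissive, and uneven splits such as 8+3 or 7+4 do pass. Section 1.2 also expects the injured partner to gain from a better relationship, so 10 against 0 is an extreme. What remains is that the rule claims to reflect a consideration which it does not implement.

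**The exception clause could rescue the case.** A version focused on one partner could arguably count as a different method of implementation. But the clause is optional, is triggered by contextual information and does not mention role. It may help, but it cannot be relied on.

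**The conditions are worded as sufficient, not necessary.** That is literally so, but an exception for unmet conditions makes sense only if they are meant as necessary.

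**The study is developmental and will not claim effectiveness.** This is true and limits the severity. It does not remove the point, because the protocol itself fixes a numerical rule for this decision.

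Two further inferences are tempting and should not be drawn:

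- Section 3.4 states that "One or both partners must report some dissatisfaction with their current relationship". A reader might conclude that up to 10 participants have little room to improve. Most outcome measures in Section 3.6.3 do not concern relationship satisfaction, and dissatisfaction is not tied to role, so this does not predict a split by role.
- Section 3.1 states that "The revised guidelines will be used for the next three couples". A reader might object that the rule pools over guideline versions. That is inherent in an openly iterative study and conflicts with no stated rule.

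**Conclusion.** The point holds as a gap between a stated consideration and the rule said to reflect it. It should be fixed, but it does not undermine the study.

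That benefit confined to one role can never satisfy condition 1 is exact arithmetic and needs no assumption beyond 10 completing couples. The size of the problem in milder cases depends on assumed response rates and on independence between partners. Over the rates tabulated, the chance of meeting condition 1 runs from 0.026 to 0.651. It is below one half in five of the seven cases, although the benefiting role would reach 6 of 10 with probability 0.633 or more in all of them. Condition 2 is affected in the same way only if ratings also divide by role.

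**What to change.** In Section 3.10, keep the pooled conditions as the rule for progressing the couple therapy. Add one explicit route: conditions 1 and 2 are also assessed within each role, each requiring more than half of the 10 partners in that role (at least 6). Condition 3 is unchanged. Meeting the role route without the pooled rule should lead only to consideration of a version focused on that partner, which matches the permissive wording already in the section. Both conditions must be included, because a role route for condition 1 alone could still be blocked by the pooled rating condition.

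The change takes a sentence or two and two extra table rows, and uses data already being collected. It should be made before the progression decision is taken.

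The downside should be stated beside the rule. Two extra routes raise the chance of meeting condition 1 by some route from about 0.02 to 0.09 when the response rate is 0.3 in both roles, and from about 0.41 to 0.61 when it is 0.5. Counts of 10 per role are also imprecise, which is a further reason to limit this route to consideration and not automatic progression.
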